7.6 Visit 5 [Extended dosing; second week of product provision)

Visit 5 will occur 7 days after Visit 4. A safety assessment will be performed via medical interview and physical exam. An assessment of smell will be performed. The second week of study product will be provided. Participants will be provided with an administration log to record date and time of drug administration.

VISIT 5 FOLLOW-UP VISIT [week two of extended dosing]				
Component	Procedure/Analysis			
ADMINISTRATIVE	 Collect/Update Contact Information Visit Questionnaire Quality of Life Survey Update Medical History and Concomitant Medications Protocol Counseling Assess/Document Adverse Events Provision of Study Product (week two supply) Schedule Next Study Visit Participant Reimbursement 			
PHYSICAL EXAM	 Targeted Physical Exam Assessment of Smell (BSIT) Vital Signs (BP) 			
BLOOD	 CBC with platelets AST, ALT Creatinine Total Bilirubin 			

Table 5: Visit 5 Follow-up Visit Procedures

Participants will be contacted in between Visit 5 and Visit 6 to assess for adverse events. This contact will be considered visit 5a.

7.7 Visit 6

Visit 6 will occur approximately 13 days after Visit 4. Every effort will be made to time the study visit for 24 hours after the last self-administered dose. At this visit, a safety assessment will be performed via medical interview, targeted physical exam, and repeat blood tests. An assessment of participant smell will be performed using the BSIT. Blood and respiratory samples will be collected. An acceptability questionnaire will be administered. Participants have the option to have a rectal swab collected.

VISIT & FULLOW-UP VISIT [24 nours after last self-administered dose]				
Component	Procedure/Analysis			
ADMINISTRATIVE	 Collect/Update Contact Information Visit Questionnaire Quality of Life Survey Update Medical History and Concomitant Medications Protocol Counseling Assess/Document Adverse Events Schedule Next Study Visit Participant Reimbursement Q-GRFT level 			
BLOOD	 ADA test for Anti Q-GRFT antibodies CBC with platelets AST, ALT Creatinine Total Bilirubin 			
ACCEPTABILITY	Acceptability Questionnaire			
URINE	Pregnancy test (participants of childbearing potential)			
NASAL	Q-GRFT level			
OROPHARYNGEAL	Q-GRFT level			
NASOPHARYNGEAL	Q-GRFT level			
RECTAL (optional)	Q-GRFT level			
PHYSICAL EXAM	 Targeted Physical Exam Assessment of Smell (BSIT) Vital Signs (BP) 			

T	able	6:	Visit	6	Follow	-up	Visit	Ρ	rocedu	ires
		17							la a coma	- 44 -

7.8 Visit 7

Visit 7 will occur 28 days after Visit 4. At this visit, a final safety assessment will be performed via medical interview, targeted physical exam, and repeat blood tests. An assessment of participant smell will be performed using the BSIT. Samples (blood and respiratory) will be collected. An acceptability questionnaire will be administered.

VISIT 7 FOLLOW-UP VISIT						
Component	Procedure/Analysis					
ADMINISTRATIVE	Visit Questionnaire					
	Quality of Life Survey					
	Update Medical History and Concomitant Medications					
	Assess/Document Adverse Events					
	Participant Reimbursement					
ACCEPTABILITY	Acceptability Questionnaire					
BLOOD	Q-GRFT level					
	 ADA test for Anti Q-GRFT antibodies 					
	CBC with platelets					
	AST, ALT					
	Creatinine					
	Total Bilirubin					
URINE	 Pregnancy test (participants of childbearing potential) 					
NASAL	Q-GRFT level					
OROPHARYNGEAL	Q-GRFT level					
NASOPHARYNGEAL	Q-GRFT level					
PHYSICAL EXAM	Targeted Physical Exam					
	Assessment of Taste and Smell (BSIT)Vital Signs (BP)					

Table 7: Visit 7 Follow-up Visit Procedures

7.9 Visit Window Periods

While every attempt will be made to evaluate the participant on the protocol specified date, the following visit windows are allowable

Visit 3: 24 hours after first dose (24-48 hours)

- Visit 4: 5-49 days after Visit 3
- Visit 5: 7 days after Visit 4 (5-7 days)

Visit 6: 13 days after Visit 4 (12-13 days) *

Visit 7: 28 days after Visit 4 (25-32 days)

*If scheduling requires that the participant be seen 12 days after Visit 4 rather than 13 days after, participants will be instructed to hold the final home dose and present to the clinic the next day

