2.5 PK Data: Q-GRFT

Intranasal administration of Q-GRFT to rats and rabbits indicated low levels of Q-GRFT reach systemic circulation with this route of administration. In a rat PK/BA study of Q-GRFT, very low levels of systemic exposure were observed after QD and BID intranasal administration, with highest plasma level of 14.44 ng/mL, which corresponds to an estimated 0.15% of dose administered In a 30 day multi-dose study, rats with once daily or twice daily intranasal administration, low levels of Q-GRFT in plasma (1.02 – 21.6 ng/mL) were detected in some animals up to 14 hours post-dose. Single day intranasal administration of Q-GRFT nasal solution (same as clinical formulation) to rabbits showed mean apparent Cmax of 17.1 ng/ml (male) at a

dose of 1.5 mg and 137 ng/ml (males) and 63.2 ng/ml (females) at the 3 mg dose. Q-GRFT was eliminated with a mean terminal t1/2 of 15.8 hr (males) and 18.8 hr (females) in the 3 mg intranasal group. Repeated daily intranasal administration of Q-GRFT nasal solution to rabbits for 15 days showed that the mean apparent Cmax on Day 15 was 61.7 ng/ml (female) at a dose of 1.5 mg, and 63.3 ng/ml (males) and 147 ng/ml (females) at a dose of 3 mg. Plasma exposure to Q-GRFT was 2.5-fold greater with the BID regimen versus the QD regimen in the intranasal groups on Day 15, based on AUC_{last} values. The mean AUC_{last} was 1,866 hr*ng/ml in 3 mg dosed females and 733 hr*ng/ml in 1.5 mg dosed females on Day 15. The bioavailability of intranasal Q-GRFT is 0.1% in Phase B after repeated administrations, and therefore, accumulation is unlikely to be an issue in human studies. A slight (~2x single exposure), increase in exposure was seen with repeat dose intranasal (3 mg dose), however, this increase was statistically non-significant (P>0.05) and observed in only few animals.

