7.4 Visit 3 Follow-Up Visit

Visit 3 will occur the day after the enrollment visit. Every effort will be made to time the study visit for 24 hours after dosing. At this visit, a safety assessment will be performed via medical interview, targeted physical exam, and repeat blood tests. An assessment of participant smell will be performed using the BSIT. Samples (blood, nasal, oropharyngeal, and nasopharyngeal) will be collected, and an acceptability questionnaire will be administered.

VISIT 3 FOLLOW-UP VISIT	
Component	Procedure/Analysis
ADMINISTRATIVE	 Collect/Update Contact Information Visit Questionnaire Update Medical History and Concomitant Medications Protocol Counseling Assess/Document Adverse Events Schedule Next Study Visit Participant Reimbursement
ACCEPTABILITY	Acceptability Questionnaire
BLOOD	 Q-GRFT level CBC with platelets AST, ALT Creatinine Total Bilirubin
NASAL	Q-GRFT level
OROPHARYNGEAL	Q-GRFT level
NASOPHARYNGEAL	Q-GRFT level
PHYSICAL EXAM	 Targeted Physical Exam Assessment of Smell (BSIT) Vital Signs (BP)

Table 3: Visit 3 Follow-up Visit Procedures

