9.3.2 Secondary Endpoints

Persistence: Q-GRFT concentrations from nasopharyngeal swabs 1) collected 24 hours after a single dose and 2) collected 24 hours after 13 consecutive daily doses

Pharmacokinetics: Q-GRFT concentrations in plasma 1) 24 hours after the first dose and 2) 24 hours after the 13th consecutive daily dose

Acceptability: Self-reported assessment of qualities of the experience with the nasal spray as assessed by acceptability questionnaires. Product attributes considered likely to discourage future use by participants, will be dichotomized as having a rating of lower than 3 on a 5-point Likert scale.

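### The Visit 3 window (24-48 hours) lets late samples count as the 24-hour single-dose concentration, and the analysis does not use actual sampling time

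*Combined protocol and SAP*

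**What the plan says.** Section 9.3.2 defines the PK endpoint as "Q-GRFT concentrations in plasma 1) 24 hours after the first dose and 2) 24 hours after the 13th consecutive daily dose", and the nasopharyngeal persistence endpoint is timed in the same way. Section 9.3.3 does the same for the oropharyngeal and nares swabs.

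For the single-dose sample, section 7.4 says "Visit 3 will occur the day after the enrollment visit" and adds "Every effort will be made to time the study visit for 24 hours after dosing". Section 7.9, which lists the allowable departures, gives "Visit 3: 24 hours after first dose (24-48 hours".

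For the repeat-dose sample, section 7.9 gives "Visit 6: 13 days after Visit 4 (12-13 days". Its footnote says that a participant who has to be seen on day 12 is handled as follows: "participants will be instructed to hold the final home dose and present to the clinic the next day". Section 7.7 states a best-effort aim of 24 hours after the last self-administered dose. Neither section sets a limit in hours.

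Section 9.6.2 plans descriptive summaries of these endpoints and tests between arms. It does not mention actual sampling time, an adjustment for it, or the handling of samples taken away from 24 hours.

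**The concern.** The window for the single-dose sample starts at its target and runs to twice the target. A participant who returns at 23 hours is out of window, whereas one who returns at 47 hours is in window and, as the plan stands, is summarised as a 24-hour value. With deviations in one direction only, timing errors cannot average out.

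This matters because section 2.5 says that the duration of Q-GRFT in the human nasal mucosa is not known and will be examined in this trial. Visit 3 is the only mandatory swab in the two days after the first dose, since the 1-12 hour swabs in section 7.3 are optional. If some Visit 3 samples are late, concentrations and the proportion of detectable samples would understate persistence at the labelled time.

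**Working it through.** **Plan's own figure.** The plan gives no calculation on this point. The only figure to reproduce is the window: 48/24 = 2.0 times nominal at the upper limit, and 24/24 = 1.0 at the lower limit, so no early sample is permitted.

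**Direction.** If concentration declines after 24 hours, any sample taken between 24 and 48 hours is at or below its 24-hour value. No half-life is needed for this step.

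**Inputs for size.** Section 2.5 reports, for single-day intranasal dosing in rabbits, a "mean terminal t1/2 of 15.8 hr (males) and 18.8 hr (females) in the 3 mg intranasal group". The same section gives 7.7-9.4 h for a single IV dose in rabbits, and 26.0 and 29.0 h after 15 days of IV dosing. Using any of these for humans is an assumption. They are plasma values, while persistence is measured on swabs.

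**Formulas**, with half-life h and first-order decline:
- One sample at time t: C(t)/C(24) = 2^(-(t-24)/h). At 48 hours this is r = 2^(-24/h).
- Mean if visits spread evenly over 24-48 h: (1 - r) / (ln 2 × 24/h).
- Mean if a quarter are at 48 h and the rest at 24 h: 0.75 + 0.25r.

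**Results, intranasal half-lives**

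| | h = 15.8 | h = 18.8 |
|---|---|---|
| One sample at 48 h | 2^(-1.519) = 0.349 | 2^(-1.277) = 0.413 |
| Even spread, mean | 0.6511/1.0529 = 0.618 | 0.5872/0.8849 = 0.664 |
| A quarter at 48 h, mean | 0.75 + 0.25 × 0.349 = 0.837 | 0.75 + 0.25 × 0.413 = 0.853 |

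**Sensitivity to half-life.** One sample at 48 h would be 0.12-0.17 of its 24-hour value with the single-dose IV half-lives (7.7-9.4 h), and 0.53-0.56 with the day-15 IV half-lives (26-29 h). The direction is the same throughout.

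**Visit 6.** Its window counts days from Visit 4, not hours from the last dose, and that dose is normally taken at home. A sample can therefore fall before or after 24 hours, and a missed last dose would make it later. The day-12 footnote can be read as a sample about 24 hours after the last dose or, if holding a dose and coming the next day are taken literally, about 48 hours after it.

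**The case against.** The case against is substantial. Section 7.4 gives a target and section 7.9 a tolerance around it, so the two are not a flat contradiction, and the protocol commits staff to aim for 24 hours. Most visits may be close to time. The half-lives are rabbit plasma values. Section 2.5 also reports no detectable plasma Q-GRFT in the human rectal study and expects little nasal absorption. If plasma is below quantification at both 24 and 48 hours, timing changes nothing in the plasma result.

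All of this limits the size. It does not remove the point, because a best-effort aim sets no bound and the analysis section has no rule for a late sample.

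A reader might go further and infer that Visit 3 runs late while Visit 6 is on time, so that timing alone would imitate accumulation by a factor of 1/0.413 = 2.4 to 1/0.349 = 2.9. The documents do not support that:
- Visit 6 has no hour window, so it cannot be taken as on time.
- The factor needs every Visit 3 sample at 48 hours and every Visit 6 sample at 24 hours.
- Accumulation is not an objective, and section 9.6.2 plans no test of single against repeat dosing.
- The roughly twofold rise with repeat dosing in rabbits is an exposure figure, not a 24-hour concentration. Section 2.5 calls it non-significant and seen in few animals, and considers accumulation unlikely to be an issue in humans.

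**Conclusion.** The point holds for the single-dose result. As written, samples taken up to 48 hours after the first dose are summarised as 24-hour values, and every permitted error is late. Provided levels fall after 24 hours, reported concentrations and detection rates at that time are biased low.

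The documents do not fix the size. Under the rabbit intranasal half-lives and first-order decline, a sample at the limit retains 35-41% of its 24-hour value. The group mean would be about 62-66% of the true value with an even spread of visits, and about 84-85% with a quarter at the limit. These are scenarios, not forecasts.

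The reach is limited to the descriptive single-dose summaries, the active-arm values in the between-arm comparison at Visit 3, and any informal reading of Visit 3 beside Visit 6. The primary safety endpoint is untouched.

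**What to change.** Keep 24-48 hours as the window for the Visit 3 safety assessments. For the Q-GRFT blood and swab samples:

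- Record the actual hours since the last dose at Visits 3 and 6. The first dose is given in clinic, and home doses are entered with date and time in the administration log (sections 7.5 and 7.6), so the information is obtainable.
- Set a two-sided sampling window around 24 hours at both visits, with its width justified by the sponsor. As a guide only, under the same half-lives a sample 2 hours late is 2^(-2/15.8) = 0.92 to 2^(-2/18.8) = 0.93 of its 24-hour value, and one 2 hours early is 1.08 to 1.09 times it.
- In section 9.6.2, summarise in-window samples as the 24-hour endpoint, report the others at their actual hour, and add a sensitivity summary of all samples.
- Reconcile the next-day wording in section 7.4 with the 24-48 hours in section 7.9, and the Visit 6 footnote in section 7.9 with the 24-hour aim in section 7.7.

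The cost is protocol and analysis wording, one recorded time per sample, and tighter booking. Some samples from a planned active arm of 30 will be reported outside the nominal time point. How many cannot be judged from the documents, which is why the all-samples summary should stay.

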7.10 Participants Who Become Pregnant

Urine pregnancy tests will be performed at screening, enrollment Visit 4, Visit 6, and Visit 7 for participants of pregnancy potential. Participants who become pregnant will be referred for care. Participants will remain in the study for safety but study product will be discontinued, if applicable . Pregnant participants will be contacted after their study participation to ascertain the pregnancy outcome.

7.11 Interim Visits

Interim visits may be performed at any time during the study (and study procedures repeated as clinically indicated), for the following or other reasons:

• In between screening and enrollment or Visits 3 and 4 if laboratory tests need to be repeated due to out of range values

- For administrative reasons, e.g., a participant may have questions for study staff, or may need to re-schedule a follow-up visit.
- In response to AEs. When interim contacts or visits are completed in response to participant reports of AEs, study staff will assess the reported event clinically and provide or refer the participant to appropriate medical care.
- In the event of laboratory processing issues (i.e., lost or inadequate sample)
- For other reasons at participant request.

Details of the interim visit will be recorded in the chart notes.

7.12 Clinical Evaluations and Procedures

Physical exams will include the following assessments.

A targeted physical exam will include:

- Vital signs:
 - Blood pressure
- Measurements of:
 - Weight (at Screening only)
 - Height (at Screening only)
- Visual assessment of nose and throat

A full physical exam will include the components of the targeted exam as well as the following:

- General appearance
- Cardiac exam
- Respiratory exam
- Abdomen

Additional assessments may be performed at the discretion of the examining clinician in response to symptoms or illnesses present at the time of the exam.

7.13 Laboratory Evaluations

Urine pregnancy test

Clinical and Translational Research Center University of Pittsburgh Medical Center [name]

CBC with platelets, AST, ALT, Creatinine, Total Bilirubin, SARS-CoV-2 testing

UPMC Presbyterian Shadyside CP PUH UPMC Clinical Laboratory Building [name]

Q-GRFT levels in blood, nasal, oropharyngeal, nasopharyngeal, and rectal samples and anti-Q-GRFT antibodies

[name] Laboratory, University of Louisville, Owensboro Cancer Research Program

7.14 Specimen Collection and Processing

The site will adhere to the standards of good clinical laboratory practice and site standard operating procedures for proper collection, processing, labeling, handling, transport, and storage of specimens. In cases where laboratory results are not available due to administrative or laboratory error, study staff is permitted to re-draw and/or re-collect specimens.

7.15 Biohazard Containment

As the transmission of SARS-CoV-2 can occur through contact with an asymptomatic infected individual, site staff will use appropriate personnel protective equipment per Centers for Disease Control guidance. As the transmission of HIV and other blood-borne pathogens can occur through contact with contaminated needles, blood, and blood products, appropriate blood and secretion precautions will be employed by all personnel in the drawing of blood and shipping and handling of all specimens for this study as recommended by the CDC and NIH. All biological specimens will be transported using packaging mandated by CFR 42 Part 72. Biohazardous waste will be contained according to institutional, transportation/carrier, and all other applicable regulations.

8 ASSESSMENT OF SAFETY AND CLINICAL MANAGEMENT

8.1 Safety Monitoring

The study site investigator is responsible for continuous close safety monitoring of all study participants, and for alerting the Protocol Chair if unexpected concerns arise.

8.2 Clinical Data Safety Review

Appropriate safety monitoring will be contingent upon excellent communication between study participants and study staff. Data collected from participants will include changes in medical status, concomitant medications and side effects. All adverse events will be reported as outlined in the study protocol and will be monitored by the study staff, investigators, and an Independent Safety Monitor on a regular basis. Any immediate safety concerns will be brought to the attention of the Principal Investigator. Adverse events will be reported to the IRB as required by IRB guidelines.

An Independent Safety Monitor who is familiar with the pertinent scientific literature related to intranasal medications and potential side effects will be responsible for safety monitoring. This individual will be a physician independent of the study sponsor and the principal investigators and will be available to monitor data from this single site. The Independent Safety Monitor will evaluate adverse event data on a routine basis to determine whether the study protocol should continue as originally designed, should be changed, or should be terminated. Any change to the anticipated benefit-to-risk ratio identified will be reported to the IRB. In addition, any breaches of confidentiality will be reported for review.

8.3 Adverse Events Definitions

An Adverse Event (AE) is any untoward medical occurrence in a patient or clinical investigation subject administered a pharmaceutical product that does not necessarily have a causal relationship with the study product. An AE can therefore be any unfavorable and unintended sign (including an abnormal laboratory finding), symptom, or disease temporally associated with the use of a medicinal (investigational) product, whetheror not related to the medicinal (investigational) product (see the ICH Guideline for Clinical Safety Data Management: Definitions and Standards for Expedited Reporting).

SAEs will be defined by the Manual for Expedited Reporting of Adverse Events to DAIDS (Version 2.0, January 2010), as AEs occurring at any dose that:

- Results in death
- Is life-threatening
- Requires inpatient hospitalization or prolongation of existing hospitalization
- Results in persistent or significant disability/incapacity
- Is a congenital anomaly/birth defect

• Is an important medical event that may not result in death, be immediately life-threatening, or require hospitalization but may jeopardize the participant or require intervention to prevent one of the above

Study participants will be provided instructions for contacting the study site to report any untoward medical occurrences they may experience, except for possible life-threatening events, for which they will be instructed to seek immediate emergency care. Where feasible and medically appropriate, participants will be encouraged to seek evaluation at UPMC Magee-Womens Hospital, where the study clinicians are based, and to request that a study clinician be contacted upon their arrival. All participants reporting a clinically significant untoward medical occurrence will be followed either in person or by phone until the occurrence resolves (returns to baseline) or stabilizes over a four-week period.

For each study participant, AE documentation and reporting will be undertaken throughout the scheduled duration of follow-up.

The Protocol chair/designee will grade the severity of each AE and the relationship of the AE to study product:

AE severity will be graded per the DAIDS Table for Grading Adult and Pediatric Adverse Events, Version 2.1, July 2017

It is anticipated that most AEs will not be specifically identified in the DAIDS toxicity table and will be graded by the Estimating Severity Grade for Parameters Not Identified in the Grading Table row of the toxicity table.

PARAMETER	GRADE 1 MILD	GRADE 2 MODERATE	GRADE 3 SEVERE	GRADE 4 POTENTIALLY LIFE-THREATENING
Clinical adverse event NOT identified elsewhere in the grading table	Mild symptoms causing no or minimal interference with usual social & functional activities with intervention not indicated	Moderate symptoms causing greater than minimal interference with usual social & functional activities with intervention indicated	Severe symptoms causing inability to perform usual social & functional activities with intervention or hospitalization indicated	Potentially life-threatening symptoms causing inability to perform basic self-care functions with intervention indicated to prevent permanent impairment, persistent disability, or death

Table 8: DAIDS toxicity table

Relatedness is an assessment made by a study clinician of whether the event is related to the study agent. Degrees of relatedness will be categorized according to current DAIDS-approved guidelines. Per the Manual for Expedited Reporting of Adverse Events to DAIDS (Version 2.0, January 2010), the relationship categories that will be used for this study are:

- *Related:* There is a reasonable possibility that the AE may be related to the study agent(s)
- Not Related: There is not a reasonable possibility that the AE is related to the study agent(s)

All AEs will be captured through REDCap on an AE log form. The form should be reviewed at each study visit and updated as needed. For any serious AEs (SAEs) that are continuing at a participant's study exit visit, the Protocol chair or designee must establish a clinically appropriate follow-up plan for the AE. At a minimum, the AE must be re-assessed by study staff at least 2 weeks after the participant's study exit visit; additional evaluations also may take place at the discretion of the PI/designee. The same approach must be taken for any AEs deemed related to study product that are found to have increased in severity at the study exit visit. For those AEs requiring re- assessment, if the AE has not resolved or stabilized at the time of re-assessment, study staff will continue to re-assess the participant at least once per month while the study is ongoing. After the study has ended, all AEs requiring re-assessment will be re-assessed at least once within the 30-60 days after the study end date.

